9 GENERAL STATISTICAL METHODOLOGY

All subjects who are treated will be evaluated for safety regardless of whether or not the procedure is aborted or the patient withdraws prior to the completion of all post-treatment evaluations.

Continuous data will be summarized using descriptive statistics: mean, standard deviation, median, minimum and maximum. Categorical variables will be summarized using frequency counts and percentages. For events which can occur more than once in a single subject (e.g., adverse events), the percentage will be based on subjects experiencing the event, and both patient and event counts will be reported. All hypothesis testing will be performed using a two-sided test at a 0.05 level of significance or a one-sided test at a 0.025 level of significance.

Data will be analyzed on an intent-to-treat (ITT) basis, under which analyses will be performed according to randomized assignment irrespective of the treatment actually received.

Consented patients who withdraw consent prior to randomization, or who are found not to meet the inclusion/exclusion criteria prior to randomization will not be included in the ITT population. The primary analysis will consist of all available data evaluated under ITT principles, referred to in ICH E9 (“Statistical Principles for Clinical Trials”) as the full analysis set. An as-treated analysis will also be performed for the primary efficacy endpoint which will report results based on treatment actually received irrespective of randomization.

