12. Grade II or higher spondylolisthesis.
13. Motor deficit or disabling back and/or leg pain from causes other than LSS neurogenic claudication (e.g. acute compression fracture, metabolic neuropathy, or vascular claudication symptoms, etc.).
14. Unable to walk \geq 10 feet unaided before being limited by pain. In this context, 'unaided' means without the use of a cane, walker, railing, wall, another person or any other means of walking assistance.
15. Previously randomized and/or treated in a similar clinical study.
16. Epidural lipomatosis (if it is deemed to be a significant contributor of canal narrowing by the medical monitor and the treating physician).
17. On (or pending) Workman's Compensation or in active litigation or known to be considering litigation associated with back pain.

Statistical Analysis:

Continuous data will be summarized using descriptive statistics: mean, standard deviation, median, minimum and maximum. Categorical variables will be summarized using frequency counts and percentages. For events that can occur more than once in a single subject (e.g., adverse events), the percentage will be based on subjects experiencing the event, and both patient and event counts will be reported. All hypothesis testing will be performed using a two-sided test at a 0.05 level of significance or a one-sided test at a 0.025 level of significance.

[figure not shown]
[figure not shown]
[figure not shown]
[figure not shown]
[figure not shown]
[figure not shown]
[figure not shown]
Data will be analyzed on an Intent-to-Treat basis, under which analyses will be performed according to randomized assignment irrespective of the treatment actually received.

Consented patients who withdraw consent prior to randomization, or who are found not to meet the inclusion/exclusion criteria prior to randomization will not be included in the Intent-to-Treat population. The primary analysis will consist of all available data evaluated under Intent-to-Treat principles, referred to in ICH E9 ("Statistical Principles for Clinical Trials") as the *full analysis set*. An "as treated" analysis will also be performed which will report results based on treatment actually received.

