9.1 PRIMARY EFFICACY ENDPOINT

The study will test the hypothesis that the primary endpoint among subjects randomized to the MILD arm will have superior (that is, more favorable changes on the ODI) outcomes compared to those randomized to CMM. Rejection of the below null hypothesis is consistent with the superiority of the MILD treatment:

$$H_0: \mu_{MILD} - \mu_{CMM} \leq 0$$

$$H_A: \mu_{MILD} - \mu_{CMM} > 0$$

where μ_{MILD} and μ_{CMM} are the mean values of the primary endpoint as defined above, for subjects in the MILD and CMM groups, respectively. Since lower scores represent favorable outcomes in the ODI scoring system, the endpoint is defined using baseline score minus follow-up score, so that positive values indicate improvement from baseline.

[figure not shown]

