13.5 PROTOCOL ADHERENCE / DEVIATIONS

The protocol, as written, must be followed. If the medical condition of a patient necessitates a major deviation from the protocol, the protocol deviation must be approved by the SPI and clearly documented.

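### Does the supplementary as-treated analysis need a stated rule on how it is to be read?

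*Combined protocol and SAP*

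**What the plan says.** Section 9 sets ITT as the governing principle: "analyses will be performed according to randomized assignment irrespective of the treatment actually received". It names the ITT analysis of all available data as primary. It then adds an as-treated analysis, limited to the primary efficacy endpoint, "which will report results based on treatment actually received irrespective of randomization". The statistical part of the synopsis says only that an as-treated "analysis will also be performed which will report results based on treatment actually received", without the limit to the primary endpoint.

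On testing, Section 9 states that "All hypothesis testing will be performed using a two-sided test at a 0.05 level of significance", or one-sided at 0.025. Section 9.1 writes the superiority hypothesis for randomised groups: "The study will test the hypothesis that the primary endpoint among subjects randomized to the MILD arm will have superior" outcomes to those randomised to CMM.

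On adherence, Section 6.4 has subjects treated as randomised, and the synopsis defines the control arm as excluding MILD. Section 13.5 says "The protocol, as written, must be followed". It provides for one exception, which needs approval and documentation: "If the medical condition of a patient necessitates a major deviation from the protocol".

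On aborted procedures, Section 9 speaks only to safety: "All subjects who are treated will be evaluated for safety regardless of whether or not the procedure is aborted".

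**The concern.** An as-treated comparison gives up the protection of randomisation. Section 13.5 ties the deviations it permits to the patient's medical condition. If such a deviation decided whether a subject had MILD before the endpoint visit, receipt would depend on prognosis and the contrast would mix the treatment effect with selection.

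The bias need not be conservative. If poor-prognosis subjects in the MILD arm go untreated, they move into the untreated group. MILD then looks better even when it has no effect. If poor-prognosis CMM subjects cross over to MILD, the contrast understates a real effect.

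The visible text does not call the analysis descriptive, and the general sentence on significance levels makes no exception for it. It also does not say whether an aborted procedure counts as MILD received for efficacy. At stake would be an as-treated difference presented as confirming or contradicting ITT when it only reflects who departed from assignment.

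**Working it through.** **What the plan assigns to the as-treated analysis.**

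- Status: it is performed in addition to an analysis that is named primary, so it is supplementary.
- Hypothesis: the only visible one (Section 9.1) concerns subjects by randomised arm. None is written for groups by treatment received.
- Output: the analysis reports results, and Section 9 itself says that it disregards randomisation. Section 9 already prescribes mean, SD, median, minimum and maximum for continuous data.
- Testing: the sentence on significance levels fixes the level of whatever is tested. It does not say that every summary is tested.

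**How large the distortion could be.** The documents supply up to 150 subjects (Section 5.1) and 1:1 allocation (Section 6.2), hence 75 per arm. Everything else is assumed: SD 17 ODI points, a selection score correlated ρ = 0.3, 0.5 or 0.7 with improvement, and the k worst-scoring subjects of one arm departing from assignment. With no departures the two groupings coincide and as-treated equals ITT.

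Let m_k be the mean distance below zero of the k lowest of 75 standard normal scores. If k subjects in the MILD arm go untreated and there is no effect, the treated mean rises by ρ × 17 × m_k × k/(75 − k). The untreated mean falls by ρ × 17 × m_k × k/(75 + k). So

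bias = ρ × 17 × m_k × k × [1/(75 − k) + 1/(75 + k)].

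- k = 2, m = 2.217: 17 × 2.217 × 2 × (1/73 + 1/77) = 2.01ρ, or +0.6, +1.0, +1.4 points.
- k = 4, m = 1.980: 17 × 1.980 × 4 × (1/71 + 1/79) = 3.60ρ, or +1.1, +1.8, +2.5 points.
- k = 8, m = 1.693: 17 × 1.693 × 8 × (1/67 + 1/83) = 6.21ρ, or +1.9, +3.1, +4.4 points (4.35 before rounding).

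If a one-sided 0.025 test were applied, which the plan does not prescribe for this analysis, simulated apparent superiority would be roughly:

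| MILD subjects untreated | ρ = 0.3 | ρ = 0.5 | ρ = 0.7 |
|---|---|---|---|
| 2 of 75 | 4% | 5% | 7% |
| 4 of 75 | 6% | 9–10% | 14% |
| 8 of 75 | 10% | 19–20% | 34–35% |

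ITT stays near 2.5% throughout. With noisier selection and 10% random dropout the rows become 3.4/4.5/5.1%, 4.5/6.3/8.4% and 6.4/11/17%.

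In the other direction, take a true effect of 8 points with the 15 worst-prognosis CMM subjects of 75 receiving MILD. The bias has the same form with the sign reversed: 17 × 1.381 × 15 × (1/60 + 1/90) = 9.78ρ. As-treated gives 8 − 9.78ρ = 5.1, 3.1, 1.2 points. ITT gives 8 × 60/75 = 6.4. If selection is unrelated to outcome (ρ = 0), as-treated returns 8.0.

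A different model, in which those who depart differ from the rest by ±0.5 SD, also shows both directions. With no effect and about 10% of the MILD arm untreated, the as-treated mean is −0.09 to +0.10 SD.

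**Whether a complier estimate would be better.** Dividing the ITT difference by the difference in receipt removes selection bias only if assignment acts solely through receipt. Take 20% of CMM subjects crossing over and a true effect of 8:

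- If assignment alone shifts reported ODI by 2 points, ITT is 0.8 × 8 + 2 = 8.4 and the complier estimate is 8.4/0.8 = 10.5.
- If those who cross over gain only half the effect, ITT is 8 − 0.2 × 4 = 7.2 and the complier estimate is 7.2/0.8 = 9.0.
- Its standard error is 3.47, against 2.67–2.74 for ITT, which is 27–31% wider at the unrounded values.

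**The case for a change.** The strongest case for a change is that the sponsor has committed to report this analysis, subjects know whether they had the procedure, and the outcome is a questionnaire. A sentence written before results are seen, saying that the as-treated result is descriptive and that superiority rests on ITT, costs almost nothing. It would stop a favourable as-treated figure from being given too much weight. Because the sentence on significance levels makes no exception, a test of the as-treated contrast would not breach the visible text. Whether aborted procedures count as received also affects the grouping.

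The statistical core of this stands. The contrast can be confounded in either direction, and no visible sentence labels it descriptive. The rest is weaker:

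- Section 13.5 is a general deviation clause that needs approval. It does not mention receiving or forgoing MILD, and no departure rate appears anywhere.
- The larger rates above need exact selection of the worst scorers, a strong correlation, complete outcome data and a test that the plan does not assign.
- Section 9 treats subjects with aborted procedures as treated for safety. That suggests a convention for efficacy without settling it.
- The missing limit in the synopsis is abbreviation. Section 9 carries the full statement.
- The synopsis statistics and Sections 9.1 and 9.2 are partly blacked out or lost, and Sections 6.6 and 6.7 do not appear in the public text. Silence there is poor evidence of a gap.

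**Conclusion.** No change is needed. Followed as written, the plan bases its superiority conclusion on randomised groups and reports the as-treated result beside it as a supplement that openly sets randomisation aside. The missing label is the kind of detail an analyst fills sensibly: a summary by treatment received, with departures from assignment listed by arm. The sponsor may write this down and repeat the primary-endpoint limit in the synopsis, but the conclusion does not depend on it.

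The size is zero for the primary test and conclusion. For the supplementary figure it is zero without departures. It is at most about 1.4 points with 2 of 75 MILD subjects untreated, and 1.1 to 2.5 points with 4 of 75. These figures assume SD 17, correlations of 0.3 to 0.7 and strict selection of the worst scorers, none of which the documents supply. They therefore give no threshold at which the distortion becomes material.

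A complier estimate would be a trade-off without clear gain. Its key assumption is doubtful when subjects know their treatment and report their own outcome, and it can itself overstate benefit.

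This conclusion would change only if text not visible here gave the as-treated analysis a confirmatory test or claim.

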9.1 PRIMARY EFFICACY ENDPOINT

The study will test the hypothesis that the primary endpoint among subjects randomized to the MILD arm will have superior (that is, more favorable changes on the ODI) outcomes compared to those randomized to CMM. Rejection of the below null hypothesis is consistent with the superiority of the MILD treatment:

$$H_0: \mu_{MILD} - \mu_{CMM} \leq 0$$

$$H_A: \mu_{MILD} - \mu_{CMM} > 0$$

where μ_{MILD} and μ_{CMM} are the mean values of the primary endpoint as defined above, for subjects in the MILD and CMM groups, respectively. Since lower scores represent favorable outcomes in the ODI scoring system, the endpoint is defined using baseline score minus follow-up score, so that positive values indicate improvement from baseline.

[figure not shown]

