1 PROTOCOL SYNOPSIS

Vertos MEDICAL		PROTOCOL SYNOPSIS
Title: The MOTION™ Study		
Purpose:	[REDACTED]	
Study Design: Prospective, multicenter, randomized controlled clinical study examining functional improvement in lumbar spinal stenosis (LSS) patients with neurogenic claudication who are treated with the MILD procedure plus conventional medical management (CMM), Study Group, compared to those treated with CMM alone, as the control.		
Objective: To evaluate long-term functional improvement following treatment with MILD plus CMM, compared to CMM alone in subjects with painful LSS and neurogenic claudication.		
Number of Subjects: Approximately 150 subjects	Number of Study Centers: Up to 20 centers in US	
[REDACTED]		
Randomization:		

Control Group: CMM alone (without MILD). [REDACTED]

Treatment Group: MILD plus CMM.

Entry Criteria

Inclusion Criteria:

1. Age 50-80
2. Patients experiencing neurogenic claudication symptoms for at least 3 months duration.

[REDACTED]

[REDACTED]

[REDACTED]

[REDACTED]

b. Radiologic evidence of LSS with unilateral or bilateral ligamentum flavum $\geq 2.5\text{mm}$ in thickness² confirmed by pre-op MRI or CT performed within 12 months of baseline visit.

3. Patients with comorbid conditions commonly associated with spinal stenosis, such as osteophytes, facet hypertrophy, minor spondylolisthesis (Grade I without instability), foraminal stenosis, and/or disk protrusion may be included unless the medical monitor and the treating physician has determined that the condition is too advanced.
4. Stable opioid intake with no change during 30 days prior to enrollment.
5. Available to complete all follow-up visits.

Exclusion Criteria:

1. ODI Score < 31 (0-100 ODI Scale).
2. NPRS Score < 5 (0-10 NPRS Scale).
3. Lumbar epidural steroid injections during eight weeks prior to study enrollment.
4. Baseline analgesic medication greater than 90 milligram morphine equivalent (MME) per day.
5. Prior surgery at the same treatment level.
6. Previously received interspinous spacer at the same treatment level.
7. Previously received intradiscal procedure at the same treatment level.
8. Previously received vertebral augmentation procedure at the same treatment level.
9. Previously received the MILD procedure at the same treatment level.
10. Received radiofrequency ablation at the same or the adjacent levels within 6 months prior to study enrollment.
11. History of spinal fractures with current related pain symptoms.

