5.1 NUMBER OF SITES AND SUBJECTS

To ensure that the study is adequately powered, up to 150 subjects will be enrolled at approximately 20 sites. All sites will be located in the United States. Each participating investigational site will be allowed to enroll up to 20 subjects who meet all study eligibility criteria. Additional subjects may be enrolled with sponsor approval.

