5.4.2 Exclusion Criteria

1. ODI Score < 31 (0-100 ODI Scale).
2. NPRS Score < 5 (0-10 NPRS Scale).
3. Lumbar epidural steroid injections during eight weeks prior to study enrollment.
4. Baseline analgesic medication greater than 90 milligram morphine equivalent (MME) per day.
5. Prior surgery at the same treatment level.
6. Previously received interspinous spacer at the same treatment level.
7. Previously received intradiscal procedure at the same treatment level.
8. Previously received vertebral augmentation procedure at the same treatment level.

9. Previously received the MILD procedure at the same treatment level.
10. Received radiofrequency ablation at the same or the adjacent levels within 6 months prior to study enrollment.
11. History of spinal fractures with current related pain symptoms.
12. Grade II or higher spondylolisthesis.
13. Motor deficit or disabling back and/or leg pain from causes other than LSS neurogenic claudication (e.g. acute compression fracture, metabolic neuropathy, or vascular claudication symptoms, etc.).
14. Unable to walk \geq 10 feet unaided before being limited by pain. In this context, 'unaided' means without the use of a cane, walker, railing, wall, another person or any other means of walking assistance.
15. Previously randomized and/or treated in a similar clinical study.
16. Epidural lipomatosis (if it is deemed to be a significant contributor of canal narrowing by the medical monitor and the physician).
17. On (or pending) Workman's Compensation or in active litigation or known to be considering litigation associated with back pain.

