6.2 RANDOMIZATION

Subjects will be randomly assigned in equal number (1:1) to one of two treatment arms: 1) MILD procedure plus CMM or 2) CMM only.

Based on the information provided, the system will automatically generate the assigned treatment.

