9.2 SECONDARY ENDPOINTS

Secondary endpoints will be compared between randomized groups in an analogous fashion to the primary efficacy endpoint [REDACTED]

Safety will be reported as the incidence of all serious device/procedure related AEs, as adjudicated by an independent clinical events adjudicator. The adjudicated events will be coded using the Medical Dictionary for Regulatory Activities (MedDRA). This endpoint will be tabulated and reported by randomized group. A summary of all reported AEs will also be provided.

[REDACTED]				
[REDACTED]	[REDACTED]	[REDACTED]	[REDACTED]	[REDACTED]
[REDACTED]	[REDACTED]	[REDACTED]	[REDACTED]	[REDACTED]
[REDACTED]	[REDACTED]	[REDACTED]	[REDACTED]	[REDACTED]
[REDACTED]	[REDACTED]	[REDACTED]	[REDACTED]	[REDACTED]

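### Does Section 9.1 commit the primary ODI comparison to an analysis without baseline adjustment?

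*Combined protocol and SAP*

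**What the plan says.** Section 9.1 defines the primary outcome as a change in ODI: "the endpoint is defined using baseline score minus follow-up score, so that positive values indicate improvement from baseline". The null hypothesis is that the MILD mean minus the CMM mean is at most zero. The two parameters "are the mean values of the primary endpoint as defined above, for subjects in the MILD and CMM groups, respectively". The definition to which this refers is not visible in the public copy, and a block that is not shown follows the sentence on the sign of the change.

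Section 9 sets the error rate, a "two-sided test at a 0.05 level of significance or a one-sided test at a 0.025 level of significance", and the intent-to-treat analysis set. It names no test or model. Section 9.2 says "Secondary endpoints will be compared between randomized groups in an analogous fashion to the primary efficacy endpoint", and a redaction follows directly.

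Baseline ODI is available for every eligible subject, because Section 5.4.2 excludes scores below 31. Allocation is 1:1 (Section 6.2). The sample size is about 150 in the synopsis and up to 150 in Section 5.1.

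**The concern.** A hypothesis on the difference in mean change, with no covariate in sight, suggests a two-sample comparison of change scores. In such an analysis baseline ODI enters only by subtraction, which fixes its slope at 1. If the true slope of follow-up on baseline is below 1, the arm that starts worse by chance is credited with improvement that treatment did not cause, and the standard error is larger than it need be. With about 75 subjects per arm, both effects could matter. The secondary endpoints would inherit the weakness through the analogy in Section 9.2.

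**Working it through.** **1. Do the hypotheses exclude adjustment?** Let C be baseline minus follow-up ODI, B baseline ODI and T the arm. ANCOVA on change fits C = a + d·T + g·B + error, and its treatment estimate is

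d = (mean C in MILD − mean C in CMM) − g × (mean B in MILD − mean B in CMM).

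Randomization makes the expected baseline difference zero, so d targets the MILD mean minus the CMM mean, the parameter in Section 9.1. The unadjusted comparison is the special case g = 0. The hypotheses say nothing about g, so they fit both analyses. ANCOVA on follow-up ODI gives the same treatment effect with the sign reversed. Defining the endpoint as a change therefore does not choose between them.

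**2. Where would the choice be stated?**
- Section 9.1: the endpoint definition referred to is not visible, and a block is not shown directly after the quoted sentence.
- Synopsis, Statistical Analysis: seven blocks are not shown between the significance level and the intent-to-treat statement.
- Section 9.2: text is redacted straight after the analogy to the primary endpoint.
- Section 6.2: the system assigns treatment from information that is not shown, so any randomization factors are unknown too.

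The readable text names no test of any kind, and gives no effect size, standard deviation (SD) or power, although Section 5.1 justifies the sample size by adequate power. The silence is not specific to covariates.

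**3. The plan's own figure.** The 150 cannot be reproduced, because its inputs are not public. At 75 per arm and two-sided 0.05, before dropout, the detectable standardized difference in change is (1.960 + 0.842) × √(2/75) = 0.457 at 80% power and (1.960 + 1.282) × √(2/75) = 0.529 at 90%.

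**4. What would be at stake if the test were unadjusted?** The documents give no SDs or correlation, so all of these are assumed: baseline SD sb, follow-up SD sf, correlation r.

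Variance of change: sb² + sf² − 2·r·sb·sf. Variance under ANCOVA: sf²·(1 − r²). With equal SDs the ratio is (1 + r)/2.

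| sb, sf | r | Ratio ANCOVA/change | Slope r·sf/sb |
|---|---|---|---|
| equal | 0.3 | 0.65 | 0.30 |
| equal | 0.5 | 0.75 | 0.50 |
| equal | 0.7 | 0.85 | 0.70 |
| 12, 15 | 0.3 | 204.75/261 = 0.78 | 0.38 |
| 12, 18 | 0.7 | 165.24/165.6 = 1.00 | 1.05 |

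If the unadjusted test had 80% power (also an assumption), ANCOVA would have about 94%, 90% and 86% at ratios 0.65, 0.75 and 0.85, and still 80% at 1.00.

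**5. Does the entry floor force a slope below 1?** No. Selecting on baseline leaves a linear slope of follow-up on baseline unchanged. It reduces the baseline SD and the correlation. The last row gives 0.7 × 18/12 = 1.05. Regression to the mean also affects both arms alike under randomization.

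**6. Chance imbalance.** The standard error (SE) of the baseline difference is SD × √(2/75), which is 1.96 points at SD 12 and 2.45 at SD 15. At slope 0.5, a one-SE imbalance moves the unadjusted difference by about 1.0 to 1.2 points. In ten runs of 40,000 simulated trials with no treatment effect (75 per arm, r = 0.5, both SDs 13), one-sided type I error was about 0.025 for both methods. Among trials in which MILD started more than 1.5 SE worse, it was about 0.13 unadjusted and 0.024 with ANCOVA.

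**The case for a change.** The strongest opposing case is that Section 9 is readable and sets the test level, the analysis set and an as-treated analysis, yet mentions no covariate. Taken at face value, the hypothesis invites a plain comparison of mean change. A conditional error of 0.13 against 0.024 is not trivial, and naming baseline ODI as a covariate would take one sentence and one degree of freedom.

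Two parts of this stand. No covariate appears in the readable text, and ANCOVA is at least as precise as the change score in large samples. The inference from silence does not stand. Section 9 names no primary test either, so the same reasoning would show that the trial has no test at all. The 0.13 applies only to trials with an unfavourable imbalance and only if the test is unadjusted. Over all randomizations the unadjusted test keeps its level. Even on the worst reading this would be lost efficiency and conditional bias, not an invalid analysis.

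**Conclusion.** The concern does not hold. The public text fixes an outcome scale, a sign convention and a mean-difference hypothesis, and all three fit a baseline-adjusted analysis. It neither includes nor rules out adjustment, and the places that would settle this are withheld. The secondary endpoints follow the primary method, so nothing separate can be concluded about them.

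The size of any loss depends on an unadjusted test that the documents do not state, and on SDs and correlations that they do not give. Over the assumed values, the variance ratio runs from 0.65 (150 subjects doing the work of 150/0.65 = 231) to 1.00 (no gain). What remains is a question that anyone holding the unredacted plan can answer by reading which primary test it names. It is not an error in any rule the document states.
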